1 LIST OF ABBREVIATIONS AND DEFINITIONS OF TERMS

Abbreviation	Term
ADAS-Cog	Alzheimer's Disease Assessment Scale – Cognitive Subscale
AE	adverse event
AMP	Amplitude of the rest-activity rhythm
ANCOVA	analysis of covariance
aSE	Actigraphy sleep efficiency
ATC	anatomical therapeutic class
aWE	Actigraphy wake efficiency
BMI	body mass index
CGIC- ISWRD	Clinician's Global Impression of Change - Irregular Sleep-Wake Rhythm Disorder version
CI	confidence interval
CRF	case report form
CSR	clinical study report
E2006	lemborexant
EQ-5D-5L	EuroQOL version 5D-5L
FAS	full analysis set
IS	Interdaily Stability
ISWRD	Irregular Sleep-Wake Rhythm Disorder
IV	Intradaily Variability
LEM	lemborexant
LEM2.5	lemborexant 2.5 mg
LEM5	lemborexant 5 mg
LEM10	lemborexant 10 mg
LEM15	lemborexant 15 mg
LS	least squares
OLE	Open Label Extension
MedDRA	Medical Dictionary for Regulatory Activities
MMSE	Mini Mental State Examination
NPI-10	Neuropsychiatric Inventory

Abbreviation	Term
PBO	Placebo
PD	pharmacodynamic
PK	pharmacokinetic
PSG	Polysomnography
PSQI	Pittsburgh Sleep Quality Index
RA	Relative amplitude of the rest-activity rhythm
SAE	serious adverse event
SAP	statistical analysis plan
SD	Standard deviation
SDI	Sleep Disorders Inventory
SE	Sleep efficiency (PSG)
SFI	Sleep Fragmentation Index
SI	Système International
TEAE	treatment-emergent adverse event
TIB	Time in bed
TLG	tables, listings, and graphs
WFI	Wake Fragmentation Index
WHO	World Health Organization
ZBI	Zarit Burden Interview – short form

2 INTRODUCTION

The purpose of this statistical analysis plan (SAP) is to describe the procedures and the statistical methods that will be used to analyze and report results for Eisai Protocol E2006-G000-202 open label extension (Extension Phase). Additional exploratory or post-hoc analyses not identified in this SAP may be performed to facilitate interpretation of study results and documented in the clinical study report. A separate SAP has already been finalized for the core study.

This document is prepared on the basis of the final study protocol version 10.0 (dated 20 Jun 2018). The reader is referred to the study protocol, the case report form (CRF), general CRF completion guidelines, and various data collection instruments employed in the study for details of study design, conduct, and data collection.

This SAP is to be reviewed and approved prior to study database lock. If any updates are made upon blinded review of study data or for any other reasons in the course of the study, such modifications and rationale are likewise to be documented and approved prior to unblinding of study database.

2.1 STUDY OBJECTIVES

The objective of the Extension Phase is to evaluate the long-term safety and tolerability of flexible doses of Lemborexant 5 mg (LEM5), Lemborexant 10 mg (LEM10) and Lemborexant 15 mg (LEM15) once per day over a period of 30 months in subjects with Alzheimer's disease dementia (AD-D) who have Irregular Sleep-Wake Rhythm Disorder (ISWRD).

2.2 Overall Study Design and Plan

2.2.1 Extension Phase

The Extension Phase comprises a 30-month Maintenance Period (Treatment Period) and a 14-day Follow-Up Period.

Subjects who complete the Core Study End of Study (EOS) Visit within 30 days prior to enrollment in the Extension Phase will be eligible for participation.

For subjects continuing directly from the Core Study to the Extension Phase, the End of Study (EOS) Visit of the Core Study will be the start of the Extension Phase.

Subjects who complete the Core Study, but who do not elect to immediately roll over to the Extension Phase will be required to return to the site within 30 days of completion of the Core Study and repeat selected assessments before being dispensed drug for the Extension Phase. If subjects return before 30 days of the last study visit, the tests that are required at that time are vital signs, weight, the Sleep Disorders Inventory (SDI), and the electronic Columbia-Suicide Severity Rating Scale (eC-SSRS). All other data will be carried over from Visit 6A. If subjects return on Day 30, all tests listed for Visit 6B will be performed. Details are as in (Figure 1).

During the Treatment Period, all subjects initially will receive lemborexant 10 mg per day (LEM10). At the discretion of the investigator, subjects will have the option of increasing the dose to lemborexant 15 mg per day (LEM15) or decreasing to lemborexant 5 mg per day (LEM5). All dose adjustments will be performed at an unscheduled visit or at the next scheduled visit.

All doses will be taken orally in tablet form each night for the duration of the Extension Phase immediately (ie, within 5 minutes) before the time the subject intends to sleep. The dose can be adjusted more than once during the Extension Phase. Subjects will receive 1 or 2 tablets as described below:

- LEM5: one lemborexant 5-mg tablet
- LEM10: one lemborexant 10-mg tablet
- LEM15: one lemborexant 5-mg tablet and one lemborexant 10-mg tablet

Study visits, either in person or by telephone, will be conducted according to the Schedule of Procedures and Assessments for the Extension Phase. If the phone visit indicates an ongoing adverse event (AE), the subject should be brought to the clinic for an Unscheduled Visit. Subjects may discontinue from study drug for any reason. A subject who prematurely discontinues taking study drug should return to the clinic within 2 weeks of discontinuation to complete an Early Termination (ET) Visit. The assessments of the ET Visit are the same as those for the EOS Visit for the Core Study.

If the subject discontinues from the study due to an AE, the subject must complete an ET Visit, and the AE must be followed to resolution for a period of 4 weeks, whichever comes sooner.

2.2.2 Follow-Up Period

The Follow-Up Period will be 14 to 18 days in duration and begins when subjects leave the clinic at the end of the Maintenance Period. Subjects and caregivers will return to the clinic at least 14 days but no more than 18 days after the end of the Maintenance Period for the End of Study Visit, including the recording of AEs and concomitant medications, and assessment of clinical laboratory tests, vital signs, and weight, and measurement of an electrocardiogram (ECG).

Treatment in the Extension Phase will last for a maximum duration of 30 months or until the lemborexant clinical development program for Irregular Sleep-Wake Rhythm Disorder (ISWRD) is discontinued. A study design that includes the Extension Phase is presented in [Figure 1](#).

[figure not shown]

Figure 1 Study Design

Note: Visit -1 is an optional Prescreening Period for subjects and caregivers who are unsure whether the subject has Irregular Sleep-Wake Rhythm Disorder (ISWRD). Subjects will wear an activity tracker for approximately 4 days, then return to the site to have the data from the activity tracker downloaded and analyzed to determine whether they are candidates for the study. (revised per Amendment 05)

Note: Visit 2 is a caregiver visit for downloading actigraphy data to determine eligibility; Visit 3 is the baseline visit for both subject and caregiver; Visit 4 is a visit for both subject and caregiver to download actigraphy data and perform safety assessments; Visit 5 is the end-of-treatment assessments visit; and Visit 6A is for end-of-study assessments for the Core Study. For subjects continuing directly from the Core Study into the Extension Phase, Visit 6A will be the start of the Extension Phase. Subjects who complete the Core Study, but who do not elect to immediately continue into the Extension Phase have up to 30 days after Visit 6A to participate. These subjects will be required to repeat selected assessments (Visit 6B) before being dispensed drug for the Extension Phase. Some subjects will have fewer visits based on the availability of lemborexant commercially.

ISWRD = Irregular Sleep-Wake Rhythm Disorder, V = Visit.

2.2.1 END OF EXTENSION PHASE

The End of the Extension Phase will be the date of the last study visit for the last subject in the Extension Phase.

Duration of Treatment: Up to 30 months or until the lemborexant clinical development program for ISWRD is discontinued.

3 DETERMINATION OF SAMPLE SIZE

While approximately 60 subjects will enroll in the Core Study, any subject who completed the Core Study after the protocol was amended to include the the Extension Phase will be allowed to enroll in this Extension Phase, if eligible.

4 STATISTICAL METHODS

All descriptive statistics for continuous variables will be reported using mean, standard deviation (SD), median, minimum and maximum. Categorical variables will be summarized as number (percentage) of subjects.

There will be no hypothesis testings, and data will be only be summarized by timepoint and by modal dose received by the subject.

Modal dose will be calculated as follows:

If subject has one dose start date and no dose end date, then subject has been on initial10 mg dose, model dose = 10 mg.

If a subject has start dose date and only one end date, and a second dose start date; then subject has been on 10 mg dose till first end dose date, the number of days on 10 mg is calculated as follows: first end date - first start date +1 , and number of days on the new dose is calculated as: database snapshot date- second start date +1. The modal dose is the most frequent of these two numbers, ... and so on.

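### Treatment-emergent adverse events are reported only as crude percentages by modal dose, although follow-up is unequal and tends to be longer in the LEM5 and LEM15 columns: add rates per subject-year

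*SAP*

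**What the plan says.** Section 2.1 sets the objective: long-term safety and tolerability of flexible dosing over 30 months. Section 4 rules out hypothesis tests and states that "data will be only be summarized by timepoint and by modal dose received by the subject". Sections 4.4 and 4.4.2 apply this to safety: TEAE incidence is a count and percentage of subjects by system organ class and preferred term, shown by modal dose. No subject-time denominator or time-to-first-event summary is specified.

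Follow-up differs between subjects for several stated reasons. Section 2.2.1 (Extension Phase) says: "Subjects may discontinue from study drug for any reason". The note to Figure 1 in Section 2.2.2 adds: "Some subjects will have fewer visits based on the availability of lemborexant commercially". The section on the end of the Extension Phase gives the duration of treatment as "Up to 30 months or until the lemborexant clinical development program for ISWRD is discontinued".

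On dose, Section 2.2.1 says: "During the Treatment Period, all subjects initially will receive lemborexant 10 mg per day (LEM10"). The investigator may then raise or lower it. For the modal dose after a change, Section 4 says that the "number of days on the new dose is calculated as: database snapshot date- second start date +1".

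Two other parts bear on the point. Section 4.4.1 summarises duration of exposure by modal dose. Section 4.4.2 also splits some TEAE tables by dose at first onset, within modal dose and again as counts and percentages.

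**The concern.** A crude percentage answers how many subjects had an event during whatever follow-up they had. Columns can be compared on that measure only if follow-up is similar. Here the column is partly determined by follow-up: to be classed as LEM5 or LEM15 a subject must stay on treatment long enough to change dose, whereas anyone who stops before a change stays in LEM10.

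A reader of the TEAE tables could therefore take longer observation in the LEM5 or LEM15 column for higher risk at that dose. In a descriptive safety phase these tables are the main result, so their reading matters even though nothing is tested.

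**Working it through.** **1. No figure to reproduce.** The SAP gives no event rate, drop-out rate, proportion changing dose or sample size for the Extension Phase. Section 3 says only that "approximately 60 subjects will enroll in the Core Study".

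**2. Which subjects reach which column.** A subject who stops on 10 mg has taken no other dose, so LEM10 is the only possible modal dose. (Section 4 literally covers only a subject with no dose end date; LEM10 is still the natural reading.) A subject who changes dose and then stops may go either way. Assumed example: 10 mg on days 1-60, new dose from day 61, last dose on day 75, snapshot on day 900. Days on 10 mg: 60 - 1 + 1 = 60. Days on the new dose as Section 4 writes it: 900 - 61 + 1 = 840, so the subject is classed to the new dose. Counted to the last dose: 75 - 61 + 1 = 15, so LEM10. The selection is a tendency under either count, not a rule.

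**3. Illustration with equal risk.** From the SAP: start on 10 mg and a 30-month cap. Assumed: drop-out q = 0.02, 0.03 or 0.05 per month; event hazard r = 0.01, 0.02 or 0.05 per month, the same in all columns; 30% or 50% of subjects due for one dose change at month c, independent of events.

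- Exposure d = min(Exp(q), 30); event time e = Exp(r).
- Snapshot count (month 30): new dose if c < d and 30 - c > c. End-of-dosing count: new dose if c < d and d - c > c. Otherwise LEM10.
- Crude incidence = share with e < d. First-event rate = subjects with e < d, divided by the sum of min(e, d). Approximate rate = the same subjects divided by the sum of d.

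Simulated crude ratio, changed-dose to LEM10 columns:

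| Change time | New-dose days to snapshot | New-dose days to end of dosing |
|---|---|---|
| Months 0.5-3 | 1.05-1.17 | 1.09-1.32 |
| Months 1-6 | 1.09-1.32 | 1.15-1.56 |

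Middle case (50% change in months 1-6, q = 0.03, r = 0.02):

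- Snapshot: mean exposure 18.2 v 21.7 months; 28.6% v 34.1%; 0.341/0.286 = 1.19.
- End of dosing: 17.3 v 23.4 months; 27.3% v 36.5%; 0.365/0.273 = 1.34.
- Check: incidence over all subjects is r/(r+q) × (1 - exp(-30(r+q))) = 0.4 × (1 - exp(-1.5)) = 31.1%, between the column values as it must be.

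In the same scenarios the first-event rate ratio is 0.99-1.01 and the approximate rate ratio 0.94-1.00.

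**4. Without a constant hazard.** The recovery to 1 in step 3 follows from the constant hazard. Assume instead 0.10 per month for 3 months and 0.01 afterwards, identical in all columns:

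| Scenario | Count | Crude ratio | First-event rate ratio |
|---|---|---|---|
| 50% change in months 1-6, drop-out 5% per month | Snapshot | 1.19 | 0.91 |
| | End of dosing | 1.25 | 0.81 |
| Changes continuing at 10% per month, drop-out 3% | Snapshot | 1.25 | 0.81 |
| | End of dosing | 1.29 | 0.76 |

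Across the front-loaded cases tried, the rate ratio is about 0.76-0.97 against crude ratios of 1.07-1.29; earlier changes and lower drop-out lie nearer 1. The rate can thus err in the other direction.

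**5. Precision.** The exact Poisson limits for k events in T subject-years are χ²(0.025; 2k)/(2T) and χ²(0.975; 2k+2)/(2T). An assumed 5 events in 20 subject-years gives 25 per 100 (8.1-58.3); 12 in 60 gives 20 per 100 (10.3-34.9).

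**The case against.** The strongest reply is that nothing here is wrong. Counts and percentages properly describe a single-drug, open-label phase, and the SAP nowhere says that the modal-dose columns will be compared for risk. The exposure table shows any imbalance, and dividing by it removes most of the distortion in step 3. Section 2 allows further exploratory analyses. In the middle snapshot case the gap is 34.1 - 28.6 = 5.5 points. With an assumed 30 subjects per column its standard error is √(0.286×0.714/30 + 0.341×0.659/30) = 0.12, or 12 points. Much of this stands: it makes the point an improvement of modest size. It does not remove it, because neither the exposure table nor the onset-dose tables put time at risk beside the TEAE counts.

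A reader might infer more than the SAP supports in four ways.

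- That all early leavers fall into LEM10. Step 2 shows that a subject who changes early and then stops can be classed to the new dose.
- That the distortion could double or triple the percentages. Ratios up to 2.92 arise only if dose changes continue at 5-20% per month, so that 78-99.8% of completers change dose; nothing in the SAP suggests this.
- That rates per subject-year cure the problem. Step 4 shows that they do so only under a roughly constant hazard.
- That interim and final percentages conflict. Cumulative incidence rises with follow-up in any trial, and the SAP does not set the two cuts side by side.

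**Conclusion.** The point holds as a low-priority, inexpensive improvement. Under the stated assumptions (equal constant hazards, one dose change in 30-50% of subjects within months 0.5-6, drop-out 2-5% and events 1-5% per month), crude TEAE percentages in the LEM5 and LEM15 columns would exceed those in LEM10 by a factor of about 1.05-1.3 with new-dose days counted to a month-30 snapshot. Counted to the end of dosing, the factor is about 1.1-1.6. The direction follows from the design whenever dose change is unrelated to risk; the size cannot be known from the SAP. A first-event rate is a useful companion to the percentage, not a replacement for it.

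**What to change.** In Section 4.4.2, keep the counts and percentages and add first-event rates per 100 subject-years with exact Poisson 95% intervals, by modal dose and for all Extension subjects. Cover any TEAE, serious TEAEs, TEAEs leading to discontinuation, and common preferred terms. Define time at risk from the first Extension dose to the earliest of the first event, last dose plus 14 days (the SAP's own TEAE window) and the data cut.

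Because early clustering of events would bias the rate, also give it by period (for example the first 3 months and later), or add a time-to-first-event curve. A simpler fallback is to divide the number of subjects with an event by the total exposure behind the Section 4.4.1 summary.

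The cost is one derived time variable per event category and one extra table column; the dose and onset dates are already needed for the exposure and onset-dose tables. The text should state four limits:

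- Intervals will be wide with about 60 subjects or fewer.
- Events before a dose change still count to the later modal dose.
- Dose changes prompted by adverse events are not corrected for.
- The rate assumes a roughly constant hazard, so it must be read with the percentage.

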4.3 Efficacy Analyses

SDI will be summarized by visit and modal dose based on the Safety Analysis Set.

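### The objective concerns one flexible-dose regimen, but the SAP text plans safety and SDI summaries by modal dose and commits to no all-subjects column

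*SAP*

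**What the plan says.** Section 2.1 sets the objective: to "evaluate the long-term safety and tolerability of flexible doses of Lemborexant 5 mg (LEM5), Lemborexant 10 mg (LEM10) and Lemborexant 15 mg (LEM15") over 30 months. Section 2.2.1 (Extension Phase) describes one regimen: "all subjects initially will receive lemborexant 10 mg per day (LEM10"), then "At the discretion of the investigator, subjects will have the option of increasing the dose to lemborexant 15 mg per day (LEM15) or decreasing" to LEM5, and "The dose can be adjusted more than once during the Extension Phase".

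Section 4 gives the general rule that "data will be only be summarized by timepoint and by modal dose received by the subject". It defines modal dose by counting days on each dose: "The modal dose is the most frequent of these two numbers, ... and so on".

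Section 4.3 follows the rule for efficacy: "SDI will be summarized by visit and modal dose based on the Safety Analysis Set". The opening of Section 4.4 applies modal-dose presentation to the safety data, and most of its subsections repeat it. Section 10 leaves the table shells to a separate document.

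**The concern.** The quantity that matches the objective is the result in all treated Extension subjects. It is also the one summary that does not depend on what happened to the dose after treatment began.

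Modal dose does depend on that. With a common start on LEM10, a subject enters the LEM5 column only through a reduction and the LEM15 column only through an increase, in each case followed by enough time on the new dose. If investigators titrate on tolerability or response, as is plausible, each column partly reflects how its subjects fared. There is no comparator against which to judge this. A reader could take differences between columns for dose effects and would have no displayed overall result to fall back on.

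**Working it through.** The SAP states no figure to reproduce: it plans no tests and gives no Extension sample size. The check reads each planned summary for its grouping and then works through what that grouping does.

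**1. Grouping named in the SAP**

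| Section | Summary | Grouping named | Combined column |
|---|---|---|---|
| 4 | General rule | Timepoint, modal dose | No |
| 4.2.2 | Disposition | All subjects, split by modal dose | No |
| 4.3 | SDI | Visit, modal dose | No |
| 4.4 (opening) | Safety data | Modal dose | No |
| 4.4.1 | Exposure | Modal dose | No |
| 4.4.2 | TEAE overview, deaths, SAEs, discontinuations, dose reductions and interruptions | Modal dose | No |
| 4.4.2 | TEAEs by SOC/PT, severity, relationship; non-serious above 5% | None named; 4.4 opening applies | No |
| 4.4.2 | Selected AE tables by dose at onset | Onset dose within modal dose | No |
| 4.4.3 | Laboratory values | Modal dose, visit | No |
| 4.4.4 | Vital signs | Treatment group (descriptive); modal dose (notable values) | No |
| 4.4.5 | ECG | Modal dose; shift tables by visit | No |
| 4.4.6 | eC-SSRS | Modal dose, visit | No |

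**2. Modal dose depends on titration and on follow-up.** Count days from the first Extension dose. Take a subject on LEM10 through day 30 and on LEM5 from day 31. By Section 4:

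- Days on LEM10 = 30 − 1 + 1 = 30.
- Days on LEM5 = snapshot day − 31 + 1 = snapshot day − 30.

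Snapshot at day 45 gives 30 against 15, so modal LEM10. Day 60 gives 30 against 30, a tie. Day 61 gives 30 against 31, so modal LEM5. An AE that began on LEM10 can therefore move from one modal column to another as follow-up lengthens. Section 5 plans interim analyses, so this could occur between an interim and the final report.

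**3. By-visit tables.** Take 30 months as 30 × 30 = 900 days, with one dose change. A subject with 449 days on LEM10 and 900 − 449 = 451 on LEM15 is modal LEM15. Up to 449/900 = 49.9% of that subject's treatment time, all of it at the start, would be shown under LEM15 while the subject was taking LEM10. This is the limit for one change, not an expected value.

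**4. What can be rebuilt from the columns.** Modal groups are mutually exclusive, so with n_k, m_k and s_k the size, mean and SD of column k, and N = Σn_k:

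- Counts: add across columns.
- Mean: M = Σ n_k m_k / N.
- SD: the square root of [Σ(n_k − 1)s_k² + Σ n_k(m_k − M)²] / (N − 1).
- Minimum and maximum: the extremes of the column values.
- Median: not recoverable. The columns show only that it lies between the smallest and largest column medians.

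**5. The 5% threshold.** Section 4.4.2 gives no denominator. Applied within a column, one subject exceeds it whenever 1/n > 0.05, that is n < 20. Applied to all subjects, with 60 assumed (the Core target in Section 3; Extension enrolment is not stated), 3/60 = 5.0% does not exceed it and 4/60 = 6.7% does. The two readings give different tables.

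**The case against.** Several points on the other side have weight.

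- **The word 'only'.** The sentence in Section 4 begins by ruling out hypothesis tests, so 'only' may contrast summarising with testing. A reader might infer that the SAP forbids a combined column; that is not established. What stands is that modal dose is the grouping named there and in Sections 4.3 and 4.4, and no combined one is.
- **The shells.** A total column is often set at shell level, and the shells are not at hand. It cannot be said that no table will carry one, only that the SAP text does not commit to it.
- **Selection on outcome.** A reader might infer that every column is selected on outcome. Section 2.2.1 states investigator discretion and no reasons for dose changes, so this is plausible but not documented. That the groups form after baseline is certain.
- **Onset-dose tables.** Section 4.4.2 adds AE tables by dose at first onset, which partly address attribution of AEs to dose. They sit within modal dose and do not cover SDI, laboratory or ECG data.
- **Precision.** A reader might measure the gap by zero-event upper limits, 1 − 0.05^(1/n): 4.9% for n = 60 against 13.9% for n = 20. These describe small groups, not lost information. Zero events in each exclusive column is zero in all subjects, and the SAP plans no such limits.
- **The threshold.** The claim that the 5% filter stops filtering needs a within-column reading that the text does not give.
- **By-dose display.** The objective names the three doses, so modal-dose columns are a reasonable secondary display. This supports keeping them, not showing them alone.

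**Conclusion.** The concern holds as a gap in the stated presentation. The objective is about one flexible-dose regimen, while the SAP text commits only to groups formed after baseline by titration and time on dose, and to no overall result for safety or SDI. If the tables are built as the text reads, pooled medians are unavailable and the other pooled statistics are left to the reader.

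No numerical size can be put on the selection between columns, because the SAP gives neither the reasons for dose changes nor their expected frequency; any simulated figure would be set by the titration rules assumed. The day-count examples are exact under Section 4 for a single dose change. The data are collected and the subject listings planned, so nothing is lost irretrievably. The conclusion rests on the SAP text alone; shells with a total column would close the gap in practice but not in the plan.

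**What to change.** Amend Sections 4, 4.3 and 4.4 so that data are summarised for all Extension subjects combined (flexible-dose lemborexant) and by modal dose, with the combined column named as the main display for the objective. In Section 4.4.2, state that the 5% threshold for non-serious TEAEs is applied to the combined column. Footnote the modal-dose columns as groups formed by post-baseline titration and descriptive only. Check that the shells agree.

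The cost is a few sentences and wider tables. It needs no new data and changes nothing in treatment or dosing.
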